4.2. Secondary Objectives

Efficacy is a secondary outcome that will be examined. The endpoints for evaluation include difference in MIDAS, 4-point verbal pain scale, and 11-point numeric pain scale scores prior to drug administration and 1 week, 6 weeks, and 3 months after drug administration.

5. STUDY DESIGN

5.1. General Approach for Evaluation of Treatment

This study will be a non-randomized, open-label phase 1 clinical trial. Participants above the age of 18 years who have an established diagnosis of intractable migraine (defined as failure of four other pharmacologic agents) and are active patients at our institution (i.e., have an appointment with a neurologic care provider during the enrollment period) will be offered enrollment. Either intolerance or side effects requiring early discontinuation or adequate trial at therapeutic dose without relief constitutes failure of therapy.

A neurological provider will perform a baseline assessment of enrolled patient's medical history and symptom scale scores, including MIDAS, 4-point verbal pain scale, and 11-point

numeric pain scales (Appendix G). An experienced neurointerventional co-investigator will inject 20 mg methylprednisolone and 40 mg lidocaine into the middle meningeal artery bilaterally. Each patient will receive a total of two doses of the 40mg lidocaine/20mg methylprednisolone co-administration of drugs (i.e., one dose administered within the left middle meningeal artery, and the other dose in the right middle meningeal artery). Immediate post-operative clinical evaluation, and evaluation at subsequent follow-up appointments with a neurological provider will involve assessment of neurological functional status, symptom scores, and occurrence of any associated adverse event at 1 week, 6 weeks, and 3 months. To evaluate the primary safety outcome, data will be analyzed to yield the prevalence of any adverse event, treatment-related adverse events, and serious and/or fatal adverse events. Data comparing pairwise differences in pre- and post-drug changes in symptom scores at 1-week, 6-week, and 3-month follow-up clinical encounters will be analyzed to assess secondary efficacy outcome.

5.2. Description of First Year Trial(s)

This study will be a non-randomized, open-label phase 1 clinical trial. Qualifying patients as described in Section 4.3 will be offered the option to be enrolled within the clinical trial, including explanation of study-related components and a pre-specified 3-month clinical follow-up duration.

5.3. Number of Subjects to be Evaluated

Up to 10 patients will be evaluated. Sample size was determined off of norms for phase 1 trials, as there lacks sufficient data to conduct a power analysis. Patients who are lost to follow-up and/or withdraw early from the study will not be replaced.

5.4. Duration of Trial and Subject Involvement

The duration of the clinical investigation will be 1 year, with patient involvement lasting approximately 4 months from enrollment to completion of clinical trial-related follow-up.

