2. PROTOCOL SUMMARY

Name of Drug(s)	Lidocaine hydrochloride (Xylocaine®-MPF); methylprednisolone sodium succinate (SOLU-MEDROL®)	
Treatment Group/Sample Size	10 total subjects	
Design	Open-label, non-randomized study	
Estimated Length of Subject Involvement	90 days	
Route of Administration	Intra-arterial	
Regimen	40 mg lidocaine/20mg methylprednisolone co-administered into each middle meningeal artery (left and right side) once	
Primary Objective	This study will evaluate the safety of a co-administration of intra-arterial lidocaine and methylprednisolone for patients with intractable migraine. In addition, an examination of pain-related symptomatic relief per pain score scales will be assessed.	
Study Population	10 adults over the age of 18 with a diagnosis of intractable migraine without aura, defined as failure of four treatment trials, will be enrolled in the study if they meet inclusion and exclusion criteria and are willing to participate in the study.	
Multicenter	No	
Blinding	None/Open-label	
Randomization	None/Non-randomized	
Primary Safety Variable	Adverse Events	
Primary Efficacy Variable	y Variable Difference in pre- and post-drug MIDAS, 4-point verbal pain scale, and 11-point numeric pain scale scores.	

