7. STUDY TREATMENT, PROCEDURES, AND GUIDELINES

7.1. Study Intervention

After baseline screening assessment, patients will be scheduled within one month for investigational drug administration. Xylocaine®-MPF will be prepared for administration of 40 mg of active lidocaine hydrochloride per dose as described in Section 3.1.4. A total of two doses (40 mg lidocaine hydrochloride per dose; 80 mg total) of lidocaine hydrochloride will be prepared for the injection of each dose into each middle meningeal artery (left and right). SOLU-MEDROL® will be prepared for administration of 20 mg of active methylprednisolone sodium succinate as described in Section 3.1.4. A total of two doses (20 mg methylprednisolone sodium succinate per dose; 40 mg total) of methylprednisolone sodium succinate will be prepared for the injection of each dose into each middle meningeal artery (left and right). No placebo agents will be used during the study. Agents will not be blinded. Agents will be prepared and stored per instructions contained within Section 16 (HOW SUPPLIED/STORAGE AND HANDLING) of the Prescribing Information and manufactures' guidelines contained within the packaging insert.

The treatment will be administered in the Acute Stroke and NeuroInterventional Suite at Cooper University Health Care. The care team will include an experienced neurointerventional physician with extensive experience in proper catheter placement and technical specifications necessary for the procedure below, certified and licensed angiography technicians, a dedicated anesthesiology care team, pharmacy team, and nursing team comprised of neurocritical care certified nurses (including post-procedural recovery and observation). Within the immediate treatment area, availability to resuscitative equipment and continuous vital sign monitoring, including rapid cycling continuous blood pressure monitoring (with measurements at least every 5 minutes), continuous pulse oximetry, respiratory rate, continuous heart rate monitor, and electrocardiographic monitoring, will be ensured. For safety, patients may be sedated using institutional monitored anesthesia care (MAC) protocol under the care of a licensed anesthesiologist, and thus will not require intubation. Patients will be monitored continuously throughout the procedure and for four hours post-operatively in a dedicated post-angiography care unit.

The following steps will be performed interprocedurally:

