7.2.2. Visit 2 (Administration)

(Week 0 – Approximately 4 weeks after Visit 1).

- 1. Record any changes to concomitant medications.
- 2. Perform a complete neurological physical exam, including visual field assessment, fundoscopic exam, cranial nerve exam, peripheral motor and sensory fields, and reflexes.
- 3. Perform and record vital signs, including blood pressure monitoring.
- 4. Administer study drug (lidocaine hydrochloride and methylprednisolone serially).
- 5. Perform clinical laboratory tests (i.e., complete metabolic blood panel) following study drug administration.
- 6. Administer migraine-related symptom scores (i.e., MIDAS, 4-point Verbal Rating Scale, 11-point Numeric Pain Rating Scale).
- 7. Review Subject Diary, including details of any migraine episodes.
- 8. Schedule subject for Visit 3.

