7.2.5. Visit 5 (Week 12 ± 2 days)

- 1. Record any changes to concomitant medications.
- 2. Perform a complete neurological physical exam, including visual field assessment, fundoscopic exam, cranial nerve exam, peripheral motor and sensory fields, and reflexes.
- 3. Perform and record vital signs, including blood pressure monitoring.
- 4. Administer migraine-related symptom scores (i.e., MIDAS, 4-point Verbal Rating Scale, 11-point Numeric Pain Rating Scale).
- 5. Review Subject Diary, including any incidence of adverse events.

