8. DATA SAFETY MONITORING

8.1. Safety Monitoring Plan

Data safety monitoring will be undertaken jointly by the Institutional Review Board and Investigator, including training all co-investigators to report research-related adverse events to Investigator within 12 hours. A safety report to the Institutional Review Board after either

reaching half of anticipated enrollment (10 subjects) or eight months following trial start, whichever event occurs first, will be prepared.

An adverse event (AE) is any untoward medical occurrence in a clinical investigation of a patient administered a pharmaceutical product and that does not necessarily have a causal relationship with the treatment. An AE is therefore any unfavorable and unintended sign (including an abnormal laboratory finding), symptom or disease temporally associated with the administration of an investigational product, whether or not related to that investigational product. An unexpected AE is one of a type not identified in nature, severity, or frequency in the current Prescribing Information or of greater severity or frequency than expected based on the information in the Prescribing Information.

The Investigator will probe, via discussion with the subject, for the occurrence of AEs during each subject visit and record the information in the site's source documents. Adverse events will be recorded in the patient study records. Adverse events will be described by duration (start and stop dates and times), severity, outcome, treatment and relation to study drug, or if unrelated, the cause.

AE Severity

The National Cancer Institute's Common Terminology Criteria for Adverse Events (CTCAE) Version 3.0 will be used to assess and grade AE severity, including laboratory abnormalities judged to be clinically significant. The modified criteria can be found in the study manual. If the experience is not covered in the modified criteria, the guidelines shown in Table 2 below should be used to grade severity.

Severity (Toxicity Grade)	Description
Mild (1)	Transient or mild discomfort; no limitation in activity; no
	medical intervention or therapy required. The subject may be
	aware of the sign or symptom but tolerates it reasonably well.
Moderate (2)	Mild to moderate limitation in activity, no or minimal medical
	intervention/therapy required.
Severe (3)	Marked limitation in activity, medical intervention/therapy
	required, hospitalizations possible.

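### The eight-month trigger for the IRB safety report falls at about the point where the trial's own timeline ends enrolment, so that report can inform few remaining dosing decisions

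*Combined protocol and SAP*

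**What the plan says.** Section 5.4 gives both lengths: "The duration of the clinical investigation will be 1 year, with patient involvement lasting approximately 4 months from enrollment". The visit schedule is consistent with the second. Section 7.2.2 places administration at "Week 0 – Approximately 4 weeks after Visit 1", Section 7.1 says "patients will be scheduled within one month for investigational drug administration", and Section 7.2.5 puts the last visit at Week 12. The summary in Section 2 differs: "Estimated Length of Subject Involvement 90 days".

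Section 8.1 makes an IRB safety report due on "reaching half of anticipated enrollment (10 subjects) or eight months following trial start, whichever event occurs first, will be prepared". Section 5.3 sets the maximum: "Up to 10 patients will be evaluated", without replacement. Section 9.2 adds one interim safety analysis, to be run once 10 patients, described there as 50%, have completed Visit 3.

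The documents give no accrual rate, do not define trial start, set no closing date for enrolment, and attach no pause in enrolment to the report.

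**The concern.** Of the two triggers in Section 8.1, the count serves a trial that recruits well. The calendar date serves one that recruits slowly, so that a review takes place even though the count has not been reached. For the review to bear on who is still to be exposed, the date has to fall while a useful number of patients are undosed.

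Here it coincides with the month in which recruitment has to end if every patient is to finish follow-up within the year. Safety is the primary objective of this phase 1 trial (Section 4.1), so the timing of its scheduled safety looks matters more than it would elsewhere.

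**Working it through.** **Inputs.** Trial length 12 months and about 4 months per patient (5.4); about 4 weeks from Visit 1 to dose (7.2.2); 12 weeks from dose to last visit (7.2.5); 90 days (Section 2); maximum 10 patients (5.3); calendar trigger at month 8 (8.1). One month = 365.25/12 = 30.44 days = 4.35 weeks, so 4 weeks = 0.92 month.

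**Step 1: the plan's own figure.** 4 + 12 = 16 weeks; 16/4.35 = 3.68 months. This agrees with the approximate 4 months in Section 5.4.

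**Step 2: end of enrolment and last dose.**
- Section 5.4 as stated: 12 − 4 = month 8.0.
- Visit schedule: 12 − 3.68 = month 8.3.
- Summary's 90 days: 90/30.44 = 2.96 months, and 12 − 2.96 = month 9.0.
- Latest dose that allows 12 weeks of follow-up: 12 − 12/4.35 = month 9.2.

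**Step 3: patients dosed at month 8.** Accrual is an assumption throughout. With even accrual from month 0, the share dosed is (8 − 0.92)/(month enrolment ends).

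| Assumption | Calculation | Dosed at month 8 |
|---|---|---|
| Even, ends month 8.0 | 7.08/8.0 | 8.85 of 10 |
| Even, ends month 8.3 | 7.08/8.32 | 8.5 of 10 |
| Even, ends month 9.0 | 7.08/9.04 | 7.8 of 10 |
| Front-loaded, (t/8)^0.5 | (7.08/8)^0.5 | 9.4 of 10 |
| Back-loaded, (t/8)^2 | (7.08/8)^2 | 7.8 of 10 |
| Back-loaded, (t/8)^3 | (7.08/8)^3 | 6.9 of 10 |
| First enrolment at month 2 | 5.08/6 | 8.5 of 10 |
| First enrolment at month 4 | 3.08/4 | 7.7 of 10 |
| First enrolment at month 6 | 1.08/2 | 5.4 of 10 |

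In whole patients, 10 enrolled every 0.8 month (0.8, 1.6, … 8.0) are dosed at 1.72, 2.52, … 8.92. Eight are dosed by month 8 and two are not. Four patients enrolled at months 2, 4, 6 and 8 are dosed at 2.92, 4.92, 6.92 and 8.92, so 3 of 4 are dosed by month 8.

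**Step 4: what the count trigger does.**
- Literal text: 10 subjects is the full sample, so the count is met only at full enrolment. The Section 9.2 interim needs 10 patients past Visit 3, which comes after the last dose. Month 8 is then the only scheduled formal safety look that can precede full enrolment.
- Count read as 5: under even accrual of 10, the fifth patient enrols at 5 × 0.8 = month 4.0. Three or four have been dosed by then (3 on the whole-patient schedule; 10 × (4.0 − 0.92)/8 = 3.85 on the continuous one). The calendar clause operates only if fewer than 5 are enrolled by month 8.

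**Step 5: an alternative calendar point, three months after the first dose.**
- Even accrual of 10: 1.72 + 3 = month 4.7; 4 dosed, 6 not.
- Four evenly spaced patients: 2.92 + 3 = month 5.9; 2 dosed, 2 not.

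**The case against.** The strongest reply is that the clause takes the earlier of two events. If half of enrolment means 5 of 10, a trial recruiting steadily produces its report near month 4 with 6 or 7 patients undosed, and month 8 never comes into play. The figure of 8 to 9 of 10 then describes a case in which the calendar clause is idle. This stands for the corrected count: there, the relevant case is slow accrual, for which the four-patient example (3 of 4) is the better guide. It does not answer the literal text, where the count is the whole sample.

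The end of enrolment at month 8 is also inferred. Section 5.4 says approximately, the visit schedule allows month 8.3, and the summary's 90 days allows month 9.0. This stands as well, and a range is the right way to report it. The 90 days is close to post-dose follow-up alone, whereas Section 5.4 counts from enrolment.

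A reader might go further and infer that nearly every dose has been given by month 8, that no dosing decision could be informed, or that the report protects almost nobody. The documents do not support this:
- Without a stated accrual rate, the dosed share at month 8 is an assumption. Even on steady accrual two of 10 may be undosed, and more if recruitment is late.
- The documents give no IRB review time, so it cannot be said that a review would arrive too late for every remaining patient.
- Other safeguards run throughout. Co-investigators report research-related events to the Investigator within 12 hours (8.1). Qualifying events go to the IRB within 7 days, with an assessment of risk-benefit and of any need to change the protocol or consent form.
- The report would still serve dosed patients who are in follow-up.

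**Conclusion.** The point holds in a limited form. On the plan's own timeline, the calendar trigger falls at about the end of recruitment, when roughly 8 to 9 of 10 patients have been dosed under even accrual from month 0 with a 4-week lag. The range is about 5 to 8 of 10 for late or back-loaded accrual, and 3 of 4 if only four patients enrol evenly. The report can therefore inform few remaining dosing decisions.

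How much this matters depends on the count in the same sentence. Left at 10, month 8 is the only scheduled formal look that can come before full enrolment, and its lateness is a real weakness. Corrected to 5, the weakness is confined to a trial with fewer than 5 patients enrolled by month 8. No stated figure is miscalculated: 12, 4 and 8 months are mutually consistent, and the defect is one of timing. It should be corrected.

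**What to change.** Amend the one sentence in Section 8.1 in two respects:

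1. Reconcile the count of 10 subjects, described as half of enrolment, with the maximum of 10 in Section 5.3. Section 9.2 needs the same reconciliation.
2. Replace the eight-month date with a calendar point inside the dosing period, for example three months after the first patient is dosed, and keep the rule that the earlier event governs.

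Anchoring to the first dose also removes the dependence on an undefined trial start. The example precedes month 8 only if the first dose is given before month 5 (8 − 3 = 5). With a later start the reconciled count has to carry the safeguard, so both changes belong together. Section 2 (90 days) and Section 5.4 (about 4 months) should be aligned at the same time.

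The cost is that the report may cover fewer patients: about 4 dosed instead of 8 to 9 under even accrual of 10 when the calendar point governs, and 2 instead of 3 in the four-patient case. Only a reporting date changes; no dose, visit or clinical rule is affected.

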6. SUBJECT SELECTION

6.1. Inclusion Criteria

1. Male or female ≥ 18 years of age.

- 2. Documentation of a diagnosis of intractable migraine without aura, including failure of at least four classes of preventative drugs. Either intolerance or side effects requiring early discontinuation or adequate trial at therapeutic dose without relief constitutes failure of therapy.
- 3. Written informed consent obtained from subject and ability for subject to comply with the requirements of the study.

6.2. Exclusion Criteria

- 1. Pregnant, breastfeeding, or unwilling to practice contraception during participation in the study. Medically acceptable contraceptives include: (1) surgical sterilization (such as a tubal ligation or hysterectomy), (2) approved hormonal contraceptives (such as birth control pills, patches, implants or injections), (3) barrier methods (such as a condom or diaphragm) used with a spermicide, or (4) an intrauterine device (IUD).
- 2. Presence of a condition or abnormality that in the opinion of the Investigator would compromise the safety of the patient or the quality of the data.
- 3. Patients with concomitant intracranial pathology (e.g., intracranial malignancy).
- 4. Blood glucose level on screening complete metabolic blood panel > 400 mg/dL.
- 5. Patients with known hypersensitivity and/or contraindication to either lidocaine hydrochloride or methylprednisolone sodium succinate, including:
 - Patients with known history of hypersensitivity to local anesthetics of the amide type.
 - Patients with systemic fungal infections.
 - Patients with known or suspected hypersensitivity to cow's milk or its components or other dairy products (SOLU-MEDROL® 40mg presentation includes lactose monohydrate, and may contain trace amounts of milk ingredients).
- 6. Patients taking chronic medications that, when co-administered with lidocaine and other local anesthetics, are at increased risk of developing methemoglobinemia: nitrates/nitrites, local anesthetics, antineoplastic agents, antibiotics, antimalarials, anticonvulsants, acetaminophen, metoclopramide, quinine, sulfasalazine.
- 7. Patients taking chronic medications that, when co-administered with methylprednisolone, are at increased risk for hypokalemia, altered drug levels, convulsions, or altered clearance: amphotericin B, diuretics, aminoglutethimide, macrolide antibiotics, anticholinesterases, antitubercular drugs, cholestyramine, cyclosporine, digitalis glycosides, estrogens (including oral contraceptives), hepatic enzyme inducers/inhibitors, and ketoconazole.
- 8. Patients have known contraindications for angiography. Patients with contrast allergy will be premedicated with diphenhydramine and steroids.
- 9. Patient has known active systemic infection or sepsis.
- 10. Patient has contraindication to anesthetic agents used for conscious sedation/monitored anesthesia care (MAC).
- 11. Concurrent participation in another research protocol for investigation of an experimental therapy.
- 12. Known or suspected inability to adhere to study protocol or protocol requirements, as per the discretion of the Investigator or treating provider.

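### Section 6.2 accepts birth control pills as contraception in exclusion 1 but excludes patients taking oral contraceptives in exclusion 7, and nothing reconciles the two

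*Combined protocol and SAP*

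**What the plan says.** Two items of Section 6.2 (Exclusion Criteria) bear on contraceptive use.

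- **Item 1** excludes anyone "Pregnant, breastfeeding, or unwilling to practice contraception during participation in the study". It then lists the methods that count as medically acceptable: surgical sterilization; "approved hormonal contraceptives (such as birth control pills, patches, implants or injections"; "barrier methods (such as a condom or diaphragm) used with a spermicide, or (4) an intrauterine device (IUD".
- **Item 7** excludes "Patients taking chronic medications that, when co-administered with methylprednisolone, are at increased risk for hypokalemia, altered drug levels, convulsions, or altered clearance". The drugs listed under that rule end with "estrogens (including oral contraceptives), hepatic enzyme inducers/inhibitors, and ketoconazole".

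The Protocol Summary (Section 2) says how the criteria combine: adults with the diagnosis "will be enrolled in the study if they meet inclusion and exclusion criteria". Section 6.3 (Recruitment) likewise offers enrolment to patients who meet both sets of criteria. No section exempts contraceptive use from item 7, restricts item 1 to methods free of estrogen, or says which item prevails.

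**The concern.** The same product is a named acceptable method in one item and a named ground for exclusion in another item of the same list. No knowledge of product composition is needed to see this for the pill, because both items name it.

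Three things are at stake.

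- **Who is exposed.** Item 7 exists because of interaction with a study drug. If staff take item 1 as permission, the trial doses a patient on a co-medication that its own safety exclusion names.
- **Who is turned away.** If staff apply item 7, they reject a patient for using a method the protocol has just called acceptable.
- **Consistency.** Two members of staff could decide the same patient differently and each cite Section 6.2.

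Safety is the primary outcome (Section 4.1), so the composition of the exposed group matters directly. The contraception rule also carries weight of its own: Section 3.4 cites fetal risk from methylprednisolone, and Table 1 in Section 7.2 schedules the pregnancy test at Visit 1 only.

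**Working it through.** The plan gives no figure to reproduce here, and the point depends on no sample size, power or error rate. The check is to apply both items to each method in item 1.

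| Method listed in item 1 | Item 1 | Item 7 | Both applied |
|---|---|---|---|
| Birth control pills | Accepted | Oral contraceptives named | Excluded: direct overlap |
| Patches, implants, injections | Accepted | Applies if the product contains estrogen; content not stated | Undetermined |
| Surgical sterilization | Accepted | Not named | No conflict shown |
| Barrier plus spermicide | Accepted | Not named | No conflict shown |
| IUD | Accepted | Not named | No conflict shown |

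**At screening.** Both items are exclusions, and a patient must clear all of them. A current pill user clears item 1 and fails item 7, so the literal result is exclusion. The pill entry in item 1 therefore describes a method whose user cannot be eligible.

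**Between screening and dosing.** Item 1 runs throughout participation. Section 7.2.2 places Visit 2, the dosing visit, about 4 weeks after Visit 1.

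1. A patient not on the pill at Visit 1 does not meet the oral contraceptive entry in item 7.
2. The patient then starts the pill, which item 1 lists as a way to meet the contraception requirement.
3. At Visit 2, Section 7.2.2 has staff note changes in co-medication before the drug is given. It states no step at which item 7 is checked again.
4. As written, the patient could be dosed while on a medication that item 7 names. Whether a newly started pill counts as chronic medication under item 7 is also not stated.

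**Size.** Section 5.3 allows up to 10 patients. With all 10 enrolled, one patient enrolled in error is 1/10 = 10% of the cohort; with fewer enrolled, the share is larger.

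**The case against.** The strongest reply is that nothing is undecidable. Item 1 excludes people unwilling to use contraception and lists what counts; it does not declare users of those methods eligible or exempt them from later items. Excluding a pill user breaks no rule, and enrolling one breaches item 7. That is right. A reader might infer that the two items cannot both be applied to one patient, or that staff must break one of them. The documents do not support either inference, because the joint reading gives a definite answer.

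Three narrower objections also stand.

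- **Scope.** It is tempting to treat every hormonal method in item 1 as in conflict. Only the pill is certain, and a patient can satisfy both items with a method that item 7 does not name.
- **Number affected.** A reader might assume that 10% to 30% of otherwise eligible patients use an estrogen-containing contraceptive and conclude that 0.10 × 10 = 1 to 0.30 × 10 = 3 of the ten places are affected. The documents give no usage rate, and the conversion does not follow. If item 7 is applied, pill users fail screening and never occupy a place, and recruitment can continue. The no-replacement rule in Section 5.3 concerns patients lost to follow-up or withdrawing early, not screen failures.
- **Visibility before dosing.** Co-medication is reviewed at both visits, and at Visit 2 that step precedes administration. A newly started pill should therefore be seen. What patients are told about contraception at consent cannot be judged from these documents.

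None of this removes the overlap. The joint reading has to be worked out by comparing two items that do not refer to each other, and item 1 read alone points the other way. Seeing a new medication at Visit 2 is not the same as being told to act on it.

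**Conclusion.** Section 6.2 contradicts itself on oral contraceptives, and nothing else in the protocol resolves it. Applied strictly, the two items exclude a pill user, so item 1 lists as acceptable a method that makes the patient ineligible. The practical risks are enrolment by staff who rely on item 1 and dosing of a patient who starts the pill after Visit 1 to meet item 1.

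The conclusion is certain for the pill, open for patches, implants and injections, and not shown for the remaining methods. How many patients would be affected cannot be estimated from the documents; each one enrolled in error would be 10% of a full cohort. The risk of inconsistent screening assumes that some staff will read item 1 without item 7. The dosing risk assumes that a recorded medication change does not by itself trigger an eligibility check. The point touches no endpoint definition, test or sample size calculation. It concerns who enters a small safety trial.

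**What to change.** Reconcile items 1 and 7 of Section 6.2 so that the accepted contraceptive methods and the excluded medications no longer overlap. The reconciled text should say where patches, implants and injections stand, and what applies to a method started after Visit 1. Use the same wording in the screening and consent materials. Which rule stands is a clinical decision for the sponsor's clinical team, and this review takes no position on it.

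The cost is a short amendment to one section with matching text in the screening and consent materials. It needs no extra patients, visits or tests.
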